### **Anthropometric parameters**

Body mass index (BMI) and waist circumference will be measured preoperative and 9 months postoperative.

### **Biochemical parameters**

Fasting blood samples will be collected from participants prior to surgery and nine months postoperative, after overnight fast and divided into two tubes; EDTA for complete blood count, the rest into plastic tubes and serum sample.

Serum glucose and Total cholesterol, HDL- cholesterol, LDL- cholesterol, and triglyceride, total protein and Albumin. Serum iron (Fe), and ferritin.

Serum insulin, Ceruloplasmin, Zn and Cu levels, CRP and lipocalin-2 (Lcn2) .

### **Statistical analysis**

All data will be analyzed with Statistical Package for the Social Sciences version 20 software (SPSS, Inc., Chicago, IL). Results will be displayed as mean  $\pm$  SD. Paired Student's t-test used to compare the data pre-operative and nine months postoperative. The chi-squared test used for category variables. Spearman correlation coefficient used to detect the correlation between different variables. Statistical correlations calculated by Pearson's correlation test.  $P < 0.05$  is considered significant.

[name]

Consultant Clinical Pathology at Alexandria University Hospitals

Alexandria University, Faculty of Medicine Alexandria University Hospitals

Mobile [contact]

Faculty contact no: [name]

Email: [contact]

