#### **Number of participants at initiating the period of study.**

They were 120 morbidly obese subjects.

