### **Preoperative and Postoperative Clinical characteristics and metabolic variables in studied subjects.**

	Preoperative	9 months postoperative	P
Body weight (Kg)	$129.7 \pm 12.1$	$93.4 \pm 13.6$	0.0013*
BMI ( $\text{kg/m}^2$ )	$47.43 \pm 5.4$	$35.7 \pm 3.8$	0.0052*
Waist circumference (cm)	$130.00 \pm 4.68$	$91.82 \pm 3.73$	0.001*

Systolic BP (mmHg)	146.0±17.0	132.0±11.0	0.001*
Total cholesterol (mmol/L)	5.85 ± 0.41	4.64 ± 0.31	0.035*
Triglycerides (mmol/L)	2.20 ± 0.23	1.92 ± 0.24	0.106
HDL cholesterol (mmol/L)	1.23 ± 0.19	1.39 ± 0.2	0.041*
LDL cholesterol (mmol/L)	3.37 ± 0.23	2.97 ± 0.21	0.022*
HOMA-IR	2.64 ± 1.3	1.44 ± 0.81	0.013*
S. Leptin (ng/ml)	102.87 ± 49.16	33.47 ±12.76	0.0001*
CRP (mg/L)	8.4±5.91	3.2±2.98	0.001*
Lipocalin 2 (µg/L)	107.24±36.8	51.6±12.73	0.001*
Albumin (g/dl)	4.05±0.21	3.91±0.29	0.113

\*Statistically significant at (p≤0.05).

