#### **Outcome measures:**

primarily was to investigate the value of zinc to copper ratio as possible biomarker of TE imbalance in morbidly obese subjects undergoing LSG.

For detection of presence of micronutrient deficiency in morbid obesity in form of zinc to copper ratio and re-evaluate it after loss of weight

Secondly to correlate it with lipocalin 2 (Lcn2) with respect to Anthropometric measurements and other metabolic markers prospectively.

As zinc to copper ratio is considered as biomarker of micronutrient status; therefore, correlate it with other biomarkers of inflammation (lipocalin 2) and other parameters as BMI, FBG to determine if micronutrient status improve after weight loss or not

**Time frame:** 9 months.

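### The planned output gives no SD or confidence interval for any within-patient change; the printed p-values cannot supply it (two contradict the table's own means and SDs), and correlations have no criterion beyond P < 0.05

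*Combined protocol and SAP*

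**What the plan says.** The Statistical analysis section is one short paragraph. On display it says "Results will be displayed as mean" ± SD. On change it says "Paired Student's t-test used to compare the data pre-operative and nine months postoperative". On association it says "Spearman correlation coefficient used to detect the correlation between different variables" and then "Statistical correlations calculated by Pearson's correlation test", without saying which coefficient applies where. The only decision rule is that P below 0.05 "is considered significant"; whether this is one- or two-sided is not stated. No mean change, SD of change, confidence interval, effect size or minimum correlation is planned.

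The table of preoperative and postoperative characteristics has the same format: a preoperative column, a "9 months postoperative" column, and P. It has 13 rows. Zinc, copper and their ratio are not among them.

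Under Outcome measures, the ratio is to be correlated with lipocalin 2, BMI and fasting glucose, "to determine if micronutrient status improve after weight loss or not".

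**The concern.** Every before/after comparison here is within patient. The precision of such a change depends on the SD of the individual differences, and the SDs at the two visits do not determine it. A reader given two visit summaries and a p-value can see roughly how far the mean moved but not how precisely that is known, nor how much patients differed in their change. A p-value can sometimes fill the gap, because the SD of the change can be worked back from it. That fails if the p-values do not fit the means and SDs beside them.

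For the correlations, a threshold on P with about 100 patients separates zero from non-zero but not weak from strong. The study's questions are how useful a marker the Zn/Cu ratio is and whether micronutrient status improves. Both call for an estimate with its uncertainty.

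**Working it through.** **Inputs.** Enrolled: "They were 120 morbidly obese subjects"; 13 did not return at 9 months. 120 − 13 = 107, and 69 women + 38 men = 107, so the plan's completer count reproduces. The preoperative BMI given for the 107 completers (47.43 ± 5.4) is the figure in the table, so both columns appear to be the same 107 patients. Means, SDs and p-values are from the table. Two-sided 0.05 is assumed. The pre/post correlation ρ is not given; 0 to 0.9 is assumed as a plausible range, and ρ = −1 is used as the mathematical limit.

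**1. Size of change.** Mean change = difference of visit means:
- triglycerides 1.92 − 2.20 = −0.28 mmol/L
- albumin 3.91 − 4.05 = −0.14 g/dl
- systolic BP 132 − 146 = −14 mmHg
- lipocalin 2 51.6 − 107.24 = −55.64 µg/L

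**2. Precision.** SD of change = √(s₁² + s₂² − 2ρs₁s₂). Half-width = t(0.975; 106) × SD/√107 = 1.983 × SD/10.344 = 0.1917 × SD.

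| Row | SD, ρ = 0 | SD, ρ = 0.9 | Half-width, ρ = 0 | Half-width, ρ = 0.9 | Ratio |
|---|---|---|---|---|---|
| Triglycerides | 0.332 | 0.106 | ±0.064 | ±0.020 | 3.1 |
| Albumin | 0.358 | 0.136 | ±0.069 | ±0.026 | 2.6 |
| Systolic BP | 20.25 | 8.57 | ±3.88 | ±1.64 | 2.4 |
| Lipocalin 2 | 38.94 | 25.94 | ±7.46 | ±4.97 | 1.5 |

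Over all 13 rows the ratio runs from 1.3 (leptin, 50.79/38.08) to about 3.1.

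**3. Can the printed p-value recover the SD?** Implied SD = |change| × √107 / t(p), where t(p) is the two-sided t value on 106 df. It cannot exceed s₁ + s₂, which is reached at ρ = −1.
- Triglycerides, p = 0.106: 0.28 × 10.344/1.630 = 1.78; maximum 0.23 + 0.24 = 0.47.
- Albumin, p = 0.113: 0.14 × 10.344/1.598 = 0.91; maximum 0.21 + 0.29 = 0.50.
- Weight, p = 0.0013: 36.3 × 10.344/3.304 = 113.6; maximum 12.1 + 13.6 = 25.7.
- Lipocalin 2, p = 0.001: 55.64 × 10.344/3.385 = 170; maximum 36.8 + 12.73 = 49.5.

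The same happens in all 13 rows: every printed p exceeds the largest value a paired t-test on 107 patients could give. Rows printed as 0.001 might reflect a reporting floor. The triglyceride and albumin rows cannot.

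**4. The two rows printed as non-significant.** With the largest possible SD:
- triglycerides −0.28 ± 0.1917 × 0.47 = −0.28 ± 0.09, so −0.37 to −0.19 (p about 1 × 10⁻⁸)
- albumin −0.14 ± 0.1917 × 0.50 = −0.14 ± 0.10, so −0.24 to −0.04 (p about 0.005)

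Rounding does not explain it. Taking the albumin change as 0.13 and the SDs as summing to 0.51 gives t = 0.13 × 10.344/0.51 = 2.64, p about 0.01.

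**5. Correlations.** Smallest significant Pearson r = t/√(t² + n − 2), with t(0.975; 105) = 1.983: r = 1.983/√(3.932 + 105) = 0.190, and R² = 0.036. Fisher interval: z = 0.1923, margin 1.96/√104 = 0.1922, so z runs from 0.0001 to 0.3845 and r from about 0.000 to 0.367. The normal approximation for Spearman gives the same threshold (0.190). Variants: n = 120 gives r = 0.179 (3.2%); one-sided at n = 107 gives r = 0.160 (2.6%).

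**The case against.** The strongest reply is that this is a reporting request. The planned tests do not change. The statistics paragraph does not itself mention visits and does not rule out a mean ± SD of the change; the per-visit reading comes from the table. A coefficient reported with n lets any reader compute the Fisher interval. And the change in lipocalin 2 is large on any assumption: at the maximum SD it is −55.6 ± 9.5 µg/L. All of that stands. It limits the point to an inexpensive improvement, but it does not supply the missing SD, and the only table in the document shows how the plan was read in practice.

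Three stronger readings are tempting, and the documents do not support them.
- A reader might infer that the size of the change is lost. It is not: it is the difference of the visit means if the same patients are in both columns, as the matching BMI suggests.
- A reader might infer that the plan treats a significant correlation as support for the ratio as a biomarker. No sentence says so; the rule only labels a result significant, and no criterion for biomarker value is given.
- A reader might cite a 47-fold uncertainty for triglycerides (±0.002 to ±0.090). That needs pre/post correlations of exactly +1 and −1; over 0 to 0.9 it is about 3-fold.

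It is also fair to say that none of these figures concerns the primary marker, because zinc, copper and their ratio are absent from the table.

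**Conclusion.** The point holds in a limited form. As displayed, the output gives the mean change by subtraction but not its precision. The 95% CI half-width is uncertain by about 1.5-fold for lipocalin 2, 2.4-fold for systolic BP, 2.6-fold for albumin and 3.1-fold for triglycerides. The printed p-values cannot close the gap, because they are incompatible with the printed means and SDs under a paired t-test on 107 patients. This affects interpretation: albumin and triglycerides are shown as not significantly changed although their intervals exclude zero at any pre/post correlation. The document does not show why. Fewer patients in some rows, another test or a transcription error are all possible, and the table gives no per-row counts.

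For correlations, the stated rule would call r = 0.19 significant, at 3.6% of variance and with an interval from about 0 to 0.37. That describes what the threshold admits; it does not show that the investigators would claim a useful marker on that basis.

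Assumptions: the same 107 patients in both columns and in every row, two-sided 0.05, and ρ between 0 and 0.9 for the half-width ratios. The triglyceride and albumin contradiction does not depend on ρ.

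**What to change.** - For Zn/Cu, Zn, Cu and every row of the preoperative/postoperative table, make the reported result the mean within-patient change with its SD, 95% CI and number of pairs, taken from the paired t-test. Keep the visit means ± SD as description.
- Recheck each printed p-value against that output, starting with triglycerides and albumin, and correct whichever of the means, SDs, counts or p-values is wrong.
- Report each correlation coefficient, labelled Pearson or Spearman, with n and a 95% CI by Fisher z (approximate for Spearman). Describe the strength of association from the estimate and its interval, not from P < 0.05 alone.

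No new patients, samples or tests are needed. The paired t-test calculation already yields the mean change, its SD and its CI, and the Fisher interval needs only r and n. The costs are a recheck of the table against the data, and that weak correlations will look less favourable.

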#### **Pre-assignment Details**

adult morbidly obese subjects were included age above 20 years, BMI above 40

Suffering from comorbidities as hypertension, DM, dyslipidemia.

Assigned participants were clinically evaluated for comorbidities as hypertension, DM, dyslipidemia.

As well as signs of nutritional deficiency as anemia, brittle nails.

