### **Group Information**

one group of participants eligible for laparoscopic sleeve gastrectomy were assigned according to their will to participate in study.

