#### **Follow-up and outcome parameters:**

All studied subjects will be followed up for early postoperative complications (within the first month) as Bleeding or Leak. Then they will be reviewed after 9 months postoperatively for assessment of anthropometric measurements, control of preoperative comorbidities, and manifestations of TE deficiencies (anemia, hair loss, teeth problems, edema. etc.).

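### The primary outcome includes detecting micronutrient deficiency, but with no limit for zinc, copper or their ratio the planned means and correlations cannot show whether it is present or how many patients enter or leave it

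*Combined protocol and SAP*

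**What the plan says.** Under Outcome measures, the text expanding on the primary aim reads: "For detection of presence of micronutrient deficiency in morbid obesity in form of zinc to copper ratio". It goes on to a re-evaluation after weight loss. The text on the secondary correlations gives their purpose as "to determine if micronutrient status improve after weight loss or not".

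Group Information describes "one group of participants eligible for laparoscopic sleeve gastrectomy". Biochemical parameters lists serum zinc and copper, with iron, ferritin and a blood count, before surgery and at nine months. It gives no reference range.

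Statistical analysis displays results as mean and SD. It compares the visits as follows: "Paired Student's t-test used to compare the data pre-operative and nine months postoperative". It adds Spearman and Pearson correlations and, for categories, "The chi-squared test used for category variables". The categories are not named.

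Clinical signs are looked for before surgery (Pre-assignment Details: "As well as signs of nutritional deficiency as anemia, brittle nails") and at nine months (Follow-up and outcome parameters). No rule links a sign to zinc, copper or the ratio.

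**The concern.** Saying that deficiency is present needs a limit or a reference population. The plan has neither, so a mean ratio before surgery cannot be called deficient or normal. A rise or fall in the mean says how the group moved on average. It does not say how many patients are below a limit at each visit, newly below it, or recovered.

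The ratio adds a difficulty of its own. It does not change if zinc and copper fall in proportion, and a low ratio can come from low zinc or from high copper.

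At stake is the wording of the main conclusion. A stable ratio or mean could be reported as preserved micronutrient status while more patients than before are low in zinc or copper.

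**Working it through.** **Inputs.** From the documents: 120 patients at the start, 13 lost, so 120 − 13 = 107 pairs; significance level 0.05. The plan states no design figure for the ratio to reproduce, and no zinc or copper values. Everything else in steps 1 to 5 is an assumption: normal values, a limit L set so that 10% are below it before surgery (z = −1.2816, 10.7 of 107), and the CVs, SD changes and correlations shown.

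**1. A mean change does not fix the share deficient.** Take a mean rise of 0.5 SD and a correlation of 0.5 between visits. The SD of the differences is √(2 − 2 × 0.5) = 1 SD, so the expected test statistic is 0.5 × √107 = 5.17 and power exceeds 99%. The share below a limit, Φ(c) before and Φ(c − 0.5) after, depends on where the limit c lies:

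| Limit c | Before | After |
|---|---|---|
| −2 SD | 2.3% | 0.6% |
| −1 SD | 15.9% | 6.7% |
| Mean | 50.0% | 30.9% |
| +1 SD | 84.1% | 69.1% |

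The same significant result fits all four rows.

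**2. Zinc and copper both fall 10% in every patient.** The ratio is 0.9 Zn / 0.9 Cu = Zn / Cu, unchanged in everyone. With baseline mean 1, L = 1 − 1.2816 × CV, and the count after is 107 × Φ((L − 0.9)/(0.9 × CV)).
- CV 20%: L = 0.7437; (0.7437 − 0.9)/0.18 = −0.868; 107 × 0.193 = 20.6.
- CV 15%: 26.5. CV 25%: 17.5.

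So about 11 becomes about 18 to 26.

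**3. Would the planned test see that fall?** Yes, if applied to zinc itself. For a 10% mean fall with CV 25% and correlation 0.3, the SD of the differences is √(0.25² + 0.225² − 2 × 0.3 × 0.25 × 0.225) = 0.282, so t = 0.1 × √107 / 0.282 = 3.7. A smaller CV or a higher correlation gives a larger t.

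**4. Cases in which the mean of zinc does not move.**
- SD larger by a factor k: the count after is 107 × Φ(−1.2816/k). For k = 1.25 this is 16.3; for k = 1.1 to 1.4 it is 13.1 to 19.3.
- Mean and SD both unchanged: newly low = recovered = 107 × [0.10 − P(both visits low)]. At correlation 0.5 this is 107 × (0.10 − 0.0324) = 7.2 each way (8.4 at 0.3, 5.7 at 0.7). Exact McNemar on 7 versus 7 gives P = 1.0. Such crossing may be ordinary variation.

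**5. Chi-squared on paired categories.** If the visits are treated as independent, the standard error of the before/after difference is too large by 1/√(1 − φ), where φ is the correlation of the two yes/no values. For correlations 0.3, 0.5 and 0.7, φ = 0.13, 0.25 and 0.41, giving factors 1.07, 1.15 and 1.30.

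**6. Separate reporting check, not part of this argument.** In the results table, the largest possible SD of the differences is the sum of the two SDs (correlation −1).
- Albumin: t = 0.14 × √107 / (0.21 + 0.29) = 2.90, so P is at most 0.0046 (0.0096 with the least favourable rounding). The table prints 0.113.
- Triglycerides: t = 0.28 × √107 / (0.23 + 0.24) = 6.16, so P is at most about 0.00000001 (about 0.00000006 with rounding). The table prints 0.106.

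**The case against.** The strongest reply is that the primary aim, read whole, treats the ratio as a possible marker of trace-element imbalance. A ratio is a natural continuous measure of that, and improvement can be read as a group-level question which the paired test and correlations answer. No section promises to classify individual patients. That reading is fair, and the planned test is sound for it. It still leaves the stated aim of detecting deficiency without an analysis.

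A reader might infer four stronger criticisms, which the documents do not support.
- *The primary test is wrong, or a real loss of zinc would go unseen.* The planned comparison covers the data generally, and zinc and copper are measured at both visits. Step 3 shows that a 10% fall would be detected. What is missing is the count and its interpretation.
- *The study needs a comparison group.* Laboratory limits would allow one group to answer the question.
- *Chi-squared has been misapplied.* The plan does not say which categories it tests. The error arises only if it compares visits, and at the same share affected it is conservative. Anemia is recorded in the same patients at both times, so that use is realistic but not stated.
- *Misclassification here is large.* The 10% prevalence, the CVs and the SD changes are assumed. The wider-spread case has no basis in the documents and would show in the printed SDs. Symmetric crossing should not be attributed to surgery.

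**Conclusion.** The point holds in a limited form. Followed exactly, the plan can test mean change in the ratio, zinc and copper, but it cannot answer the part of its primary outcome about the presence of deficiency, nor count patients who become or stop being deficient. Two parts of this do not depend on the assumed figures: without a limit or reference population nobody can be called deficient, and a proportional fall leaves the ratio unchanged. The illustrated sizes (about 11 rising to 18–26 of 107, or 13–19 with a wider spread) rest on the stated assumptions; the size in this study cannot be known from the documents. The change should be made because it is cheap and bears on the main conclusion, but it does not invalidate the planned paired analysis.

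**What to change.** In Statistical analysis:
- Keep the paired analysis, and always report zinc and copper beside the ratio.
- Add a descriptive secondary analysis, labelled post hoc because nine-month results are already reported. Give the number and percentage below the laboratory's lower limit for zinc and for copper, and above the upper limit for copper. Report this preoperatively in all 120 patients and at both visits in the 107. For the 107, add newly low and recovered counts. Give exact 95% confidence intervals.
- Use McNemar's test, not chi-squared, for any before/after category in the same patients, including anemia.
- Do not call a ratio value a deficiency unless the laboratory has a reference range for the ratio. If it has none, say so.

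The cost is a few lines and one extra table, with no new samples or visits. The drawbacks are the post hoc, descriptive status and small counts with wide intervals: 5 of 107 gives 1.5% to 10.6%, 7 newly low of 96 gives 3.0% to 14.4%, and 7 recovered of 11 gives 30.8% to 89.1%. The laboratory limits are not in the documents and must be supplied.

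As a separate matter, correct the albumin and triglyceride P-values in the results table, which are impossible with the printed means and SDs and 107 pairs.

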#### **Period of evaluation:**

First visit: preoperative for clinical assessment of participants, determine BMI and waist circumference and withdrawal of serum blood sample

Second visit: within one month after surgery to make sure that no complication occurred after surgery.

Third visit: nine months postoperative for revaluation of participants, determine BMI and waist circumference, and withdrawal of a serum blood sample

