#### **Number of participants at the end of the period of study.**

They were 107 subjects, 13 obese subject withdraw from study as they didn't come during follow up period after 9 months.

Participants according Sex (69 females, and 38 male), with the mean age of  $41.6 \pm 8.9$  years. The mean preoperative BMI was  $47.43 \pm 5.4 \text{ kg/m}^2$ . Then, they were evaluated 9 months after LSG.

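### The plan sends categorical variables to an unqualified chi-squared test and names no paired categorical method, so the test for any binary before/after change is ambiguous (minor)

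*Combined protocol and SAP*

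**What the plan says.** All references are to the combined protocol and SAP.

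- **Design.** Group Information describes "one group of participants eligible for laparoscopic sleeve gastrectomy", with no comparator. Period of evaluation sets a preoperative visit and "Third visit: nine months postoperative for revaluation of participants".
- **Methods.** Statistical analysis gives one method for the before/after comparison: "Paired Student's t-test used to compare the data pre-operative and nine months postoperative". Its next sentence is "The chi-squared test used for category variables", which does not say what is compared with what. No paired categorical method is named anywhere, and the only summary format mentioned is mean and SD.
- **Items that could be binary and paired.** Pre-assignment Details has patients evaluated for hypertension, diabetes and dyslipidemia, and adds "As well as signs of nutritional deficiency as anemia, brittle nails". At nine months, Follow-up and outcome parameters lists "control of preoperative comorbidities, and manifestations of TE deficiencies (anemia, hair loss, teeth problems, edema. etc". Biochemical parameters has blood taken "prior to surgery and nine months postoperative, after overnight fast and divided into two tubes; EDTA for complete blood count".
- **Patients with both assessments.** "They were 107 subjects, 13 obese subject withdraw from study".

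Anemia is therefore the only such item named explicitly at both times. Brittle nails are named only before surgery; hair loss, teeth problems and edema only at nine months. The comorbidities are named at baseline, but at nine months only their control is mentioned.

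**The concern.** In a one-group before/after study, the natural categorical comparison is within patients. The ordinary chi-squared test assumes independent observations. Read literally, the sentence on categorical variables would send change in anemia to that test, which could be applied in two ways, neither of them suitable:

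- **On the before and after counts**, it ignores that the same patients appear twice. When a patient's two statuses are positively correlated, the test is conservative and can miss a moderate change.
- **On the before-by-after cross-tabulation**, it asks whether the same patients tend to be anemic at both visits. A small p-value there says nothing about change and would mislead if read that way.

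At stake is the interpretation of secondary categorical parameters only.

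**Working it through.** **Inputs from the document.** Pairs: 120 − 13 = 107, which agrees with 69 women + 38 men = 107. Significance level: 0.05, taken as two-sided because the plan does not say. The plan states no power or anemia figure, so there is none to reproduce.

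**Assumed inputs.** Anemia prevalence of 20% before surgery, and 20%, 30% or 40% at nine months. Within-patient correlation phi from 0 to 0.7. None of these is in the document.

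**Why the counts version is conservative.** With prevalence p at both visits, the ordinary test takes the variance of the difference in proportions as 2p(1−p)/n. For paired data it is 2p(1−p)(1−phi)/n. The true type I error is therefore roughly 2Φ(−1.96/√(1−phi)):

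- phi 0.3: 1.96/√0.7 = 2.34, giving about 1.9%.
- phi 0.5: 1.96/√0.5 = 2.77, giving about 0.6%.

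**Exact calculation.** Every possible 2×2 paired table with n = 107 was enumerated and weighted by its multinomial probability. The four cell probabilities follow from p11 = p1·p2 + phi·√(p1(1−p1)p2(1−p2)). Writing b and c for the numbers anemic only before and only after, the tests are Pearson chi-squared without continuity correction, asymptotic McNemar (b−c)²/(b+c), and exact binomial McNemar.

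Type I error, 20% at both visits:

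| phi | Chi-squared on counts | Asymptotic McNemar | Exact McNemar |
|---|---|---|---|
| 0.2 | 2.9% | 5.3% | 3.0% |
| 0.3 | 2.0% | 5.3% | 3.0% |
| 0.5 | 0.6% | 5.0% | 2.9% |
| 0.7 | 0.05% | 4.3% | 2.2% |

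Power, 20% to 30%:

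| phi | Chi-squared on counts | Asymptotic McNemar | Exact McNemar |
|---|---|---|---|
| 0 | 40% | 39% | 33% |
| 0.2 | 39% | 47% | 39% |
| 0.4 | 37% | 60% | 50% |
| 0.6 | 34% | 77% | 70% |

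For a large change (20% to 40%, phi 0.4) the choice hardly matters: 95% for chi-squared on counts against 98% for exact McNemar.

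**Cross-tabulation.** With 20% at both visits, so no change at all, chi-squared on the cross-tabulation rejects in 53%, 97% and over 99.9% of cases at phi 0.2, 0.4 and 0.6. It is detecting association, as it should.

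**Paired t-test on 0/1 values.** In the same enumeration, its type I error and power equal those of asymptotic McNemar in every scenario tabulated.

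**Illustrative table.** Take 16 patients anemic at both visits, 4 only before, 14 only after and 73 at neither. Then 20/107 are anemic before and 30/107 after, a difference of 10/107 = 9.3 points (Newcombe paired 95% CI 1.5 to 17.3).

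- Chi-squared on counts: p = 0.106.
- Asymptotic McNemar: (4−14)²/(4+14) = 5.56, p = 0.018.
- Exact McNemar: p = 0.031.
- Chi-squared on the cross-tabulation: p ≈ 1×10⁻⁸.

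This table has phi of about 0.55, towards the upper end of the assumed range, so it shows the contrast more sharply than a low-correlation table would.

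**The case against.** **The plan already contains a valid test.** The paired t-test sentence covers the before/after data without limiting it to continuous variables. On 0/1 values that test performs like asymptotic McNemar, and on hemoglobin it is plainly suitable. This stands. A reader might infer that the plan has no valid method for change in anemia; the document does not support that. What remains is that the next sentence assigns categorical variables to a different test, and the plan does not say which sentence governs.

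**Anemia is not shown to be a binary outcome.** It is listed among clinical signs before surgery and among manifestations of deficiency afterwards. Neither section defines it, calls it present/absent, or says that the two assessments match. Blood counts at both times make a continuous measure quite plausible. This stands too: anemia is named at both times, but its form is open. Similarly, control of comorbidities may mean nine-month status among those affected at baseline, which needs no paired test.

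**No planned analysis is shown to be wrong.** The Outcome measures section lists the zinc-to-copper ratio and correlations; nothing commits to testing change in anemia. Chi-squared may be meant for subgroups such as sex, where it is valid, or loosely for McNemar's test, whose statistic is itself referred to a chi-squared distribution. A reader might infer that the investigators misuse chi-squared or that reported p-values are wrong. Neither follows, since the results table has no categorical variable.

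**The size is assumed.** True. At phi near zero the ordinary test loses nothing. Only the direction under positive correlation is independent of the assumed prevalence.

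**Conclusion.** The point holds as a minor ambiguity. The only categorical method named is unqualified and, in its ordinary form, unpaired, while the study's comparison is within patients.

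The consequence is conditional on three things: a variable is recorded as present/absent at both visits, its change is tested, and ordinary chi-squared is used. In that case, under the assumed 20% prevalence, type I error falls to about 2% (phi 0.3) or 0.6% (phi 0.5), and 23 points of power are lost against asymptotic McNemar for a 20% to 30% change at phi 0.4 (60% − 37%). The loss disappears near zero correlation and is small for large changes. The cross-tabulation version would answer a different question altogether.

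Confidence is high that no paired categorical method is named. The size of any effect is illustrative only. The primary ratio, the planned correlations and the p-values in the table of preoperative and postoperative results are untouched.

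**What to change.** Replace the chi-squared sentence in Statistical analysis with text such as:

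> Binary variables recorded by the same definition preoperatively and at nine months are compared with McNemar's test on complete pairs (asymptotic or mid-P form; exact if discordant pairs are few), with the paired difference in proportions and its 95% CI. The chi-squared test is used only to compare independent subgroups, such as by sex.

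State which variables this covers: anemia if it is recorded as present/absent, and any comorbidity so recorded at both visits. Choose the form of McNemar's test, and the rule for switching to the exact one, before looking at the tables. Using the exact form throughout is the weaker option, with type I error of only about 2% to 3% in the scenarios above.

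Because the document already reports nine-month results, label this as a change made after those data were collected.

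The cost is a sentence or two, with no new data and no change to visits. The downside is little or no gain if within-patient correlation is near zero, and asymptotic McNemar can slightly exceed the nominal level (up to 5.3% here).

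### The secondary-aim correlations pool 69 women and 38 men without adjustment, so a coefficient could reflect sex mix, or hide a within-sex association, if the Zn/Cu ratio and the marker both differ by sex

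*Combined protocol and SAP*

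**What the plan says.** Under Outcome measures in the combined protocol and SAP, the second aim is "Secondly to correlate it with lipocalin 2 (Lcn2) with respect to Anthropometric measurements and other metabolic markers prospectively". The text there goes on to name lipocalin 2, BMI and FBG as correlates.

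The method is two sentences under Statistical analysis: "Spearman correlation coefficient used to detect the correlation between different variables" and "Statistical correlations calculated by Pearson's correlation test". The section otherwise lists the paired t-test, the chi-squared test and a 0.05 threshold. Neither it nor any other section mentions partial correlation, regression, stratification or a covariate.

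Group Information describes a single group: "one group of participants eligible for laparoscopic sleeve gastrectomy were assigned according to their will to participate in study". The section on participants at the end of the study gives the make-up of those followed: "Participants according Sex (69 females, and 38 male), with the mean age of" 41.6 years (SD 8.9). Sex and age are therefore held, but serve only to describe the sample.

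The pre/post table shows both sexes combined. No zinc, copper or ratio value appears in the documents, for either sex or overall.

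**The concern.** When two variables each have different means in women and men, pooling the sexes makes them correlated even if they are unrelated within each sex. If the sex differences run in opposite directions, pooling can shrink or cancel an association that exists within each sex. Ranking does not remove this, and neither does a larger sample, because the expected pooled coefficient does not depend on n.

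At stake is the reading of the secondary aim. A coefficient produced by the 69/38 mix could be reported as evidence that the ratio tracks adiposity or inflammation, or a within-sex relation could be reported as absent. Since the plan never looks within sex or adjusts for it, its results could not show which had happened.

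**Working it through.** **No figure to reproduce.** The documents state no target correlation, power or sample-size calculation. The counts agree: 120 − 13 = 107 ("They were 120 morbidly obese subjects"; "They were 107 subjects, 13 obese subject withdraw from study") and 69 + 38 = 107.

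**Inputs from the documents.** n = 107; 69 women, 38 men; significance level 0.05. Two-sided testing is assumed, as is use of the 107 followed subjects; the sex split of all 120 is not given.

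**Inputs assumed.** d1 and d2, the sex differences in the two variables in within-sex SDs, and r_w, the within-sex correlation. The documents give none of these.

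**Pooled correlation.** With p = 69/107 = 0.645, pq = 0.645 × 0.355 = 0.229, and

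r = (r_w + pq·d1·d2) / √[(1 + pq·d1²)(1 + pq·d2²)].

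Example, r_w = 0 and d1 = d2 = 0.8: r = 0.1466 / 1.1466 = 0.128. Example, 0.3 and 1.0: r = 0.0687 / √(1.0206 × 1.2290) = 0.0687 / 1.120 = 0.061.

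**Chance of P < 0.05.** By Fisher z, atanh(r) × √(107 − 3) is set against ±1.96. For r = 0.128 this is 0.1285 × 10.198 = 1.311, giving about 26%.

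| d1 / d2 (r_w = 0) | pooled r | P < 0.05 |
|---|---|---|
| 0.3 / 0.3 | 0.02 | about 5% |
| 0.5 / 0.5 | 0.05 | about 9% |
| 0.3 / 1.0 | 0.06 | about 10% |
| 0.8 / 0.8 | 0.13 | about 26% |
| 1.0 / 1.0 | 0.19 | about 48% |

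If either d is zero, the numerator is zero and no association is created. Simulation (20,000 runs per scenario; 0.3 / 1.0 was not simulated) gave nearly the same rates, and Spearman matched Pearson closely (both about 49% at 1.0 / 1.0).

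**Masking.** Take r_w = 0.27 with differences of opposite sign. At 0.5 SD, r = (0.27 − 0.0573)/1.0573 = 0.20; at 0.8 SD, (0.27 − 0.1466)/1.1466 = 0.11; at 1.0 SD, (0.27 − 0.2290)/1.2290 = 0.03. Simulated Pearson power is 55%, 18% and 5%, against 81% when the sexes do not differ.

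**Effect of adjusting.** In the simulation, adjusting for sex alone brought rejection back to about 5% when r_w = 0, and power to about 80% at r_w = 0.27, for every pair of differences simulated. Age was not simulated.

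**Price of adjusting for sex and age.** Critical |r| = t/√(t² + df): 1.983/√(3.93 + 105) = 0.190 unadjusted, and 1.983/√(3.93 + 103) = 0.192 with two covariates. The r detectable at 80% power, tanh[(1.960 + 0.842)/√(n − 3 − k)], moves from 0.268 (k = 0) to 0.270 (k = 2).

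**Separate analysis by sex.** Detectable r is tanh(2.802/√66) = 0.33 in 69 women and tanh(2.802/√35) = 0.44 in 38 men.

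**The case against.** The strongest objection is that the premise is not in the documents. Nothing shows that the ratio, lipocalin 2, BMI or FBG differs by sex. A reader might infer that weight, waist, HDL, leptin or copper differ between women and men here, so that the correlations are in fact biased. The documents neither show nor exclude that: every tabulated value combines the sexes. Leptin is in the pre/post table but is neither in the assay list under Biochemical parameters nor named as a correlate. This stands, and limits the point to a conditional one.

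Second, each planned correlation under the second aim involves the ratio, so the ratio's own sex difference governs the effect. The larger percentages need 0.8 to 1.0 SD in both variables. This also stands, and is why the unequal case is shown.

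Third, a pooled correlation is a legitimate description of association in these patients, and the aim states no sex-conditional target. So 26% and 48% are chances of a significant pooled coefficient when nothing is present within sex; they are not inflated type I error for the marginal test. This stands, and is a reason to keep the simple coefficients.

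Fourth, no age effect can be calculated from an overall mean and SD, so a reader should not infer that age confounding has been shown.

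Fifth, the correlations might use changes from baseline, which would remove constant sex offsets. The plan does not say so, and changes would not remove sex differences in change.

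What remains is that the plan has no means of distinguishing the harmless scenarios from the serious ones, and adjustment would settle this for sex at almost no cost.

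**Conclusion.** The concern holds as a conditional weakness of the secondary aim. The planned correlations are unadjusted over a 69/38 mix of women and men. They can mislead if the ratio and a marker both differ by sex. The distortion ranges from negligible at 0.3 SD in both variables to serious from about 0.8 SD in both. Where the true case lies is unknown. These figures rest on assumed sex differences, n = 107 and two-sided testing.

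A reader might extend the point to the primary question. That does not follow: the preoperative versus nine-month comparison of the ratio is paired within person, so fixed sex does not confound it. The change is worth making, but it does not threaten the study's main comparison.

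**What to change.** In Statistical analysis:

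- Add partial Spearman correlations (or regression on ranks) adjusted for sex and age, reported beside the simple coefficients.
- State whether each correlation uses preoperative values, nine-month values or changes.
- Base any statement that the ratio tracks adiposity or inflammation on the adjusted results.
- Show the coefficients for the ratio against lipocalin 2 and against BMI separately in women and men. Label them descriptive, since each sex alone has limited power.

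Both covariates are already recorded. The cost is two degrees of freedom and a small reanalysis. Because the document already reports nine-month results, it should say that the adjusted analysis was added after data collection.
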